9.3 Safety measurements

The number and proportion of participants with at least one adverse event (AE), and the total number of AEs, will be tabulated by the treatment arm. AEs will be tabulated by diagnosis, severity and relationship to the intervention.

The number and proportion of participants who are still in hypertension care 6 months after enrolment will be tabulated by the treatment arm. Retention in care will be defined as currently having sufficient BP medicine in possession (taking into account the date of last visit and the amount of medication dispensed), as the primary definition. As a secondary definition, retention will be defined as having seen a health care worker for

hypertension in the past 3 months. Logistic regression will be used to estimate the OR and 95% CI for the effect of each intervention on retention in hypertension care. The model will include terms for treatment arm, clinic and active use of hypertension medication at baseline.

10. Additional exploratory analyses

The effect of each intervention (vs SOC) on mean change from baseline in systolic blood pressure over 12 months will be estimated using a linear mixed model. The response variable will be systolic blood pressure (at 6 and 12 months); the model will include fixed effects for treatment arm, visit, a treatment arm-visit interaction term, randomisation strata (clinic and active use of hypertension medication at enrolment) and baseline systolic blood pressure, and participant as a random effect to account for correlation of repeated measurements within the participant. The inclusion of the interaction term allows the effect of the intervention to differ over time. If the interaction term is not statistically significant at $p < 0.10$, we will drop it from the model and estimate the overall effect of each intervention (vs SOC) on the change in systolic blood pressure during the trial.

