The effect of each intervention (vs SOC) on blood pressure control over 12 months will be estimated using random effects logistic regression. The model will include fixed effects for treatment arm, visit, randomisation strata (clinic and active use of hypertension medication at enrolment) and treatment arm-visit interaction term, and random effects for the participant to account for correlation of repeated measurements. If the interaction term is not statistically significant at $p < 0.10$, we will drop it from the model and estimate the overall effect of each intervention on the blood pressure control pressure during the trial.

All participants with outcome data at either follow-up visit will be included in these analyses. Estimates from random effects models are valid under the assumption that the outcome data are missing at random conditional on the observed outcome at the non-missing visits, and other covariates in the model.

For participants with missing outcome data at month 6 or month 12, we may impute blood pressure measurements at those time points, using multiple imputation by

chained equations. Imputation models will contain observed blood pressure measurements, age, sex, BMI, smoking status, use of anti-hypertensive medication, HIV, clinic, treatment group and any covariates that are found to be associated with missingness.

The consistency of the effect of the intervention on the primary outcome will be assessed in the following pre-specified groups, using a statistical test of interaction. Effect estimates and 95% confidence intervals will be presented for each subgroup, plus the interaction p-value.

- Individuals with systolic blood pressure (SBP) ≥ 160 mmHg and those with SBP < 160 mmHg at enrolment.
- Individuals based on self-reported HIV status.
- Men and women
- Individuals aged ≥ 60 years and < 60 years.

References

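### SAP section 10 gives a between-arm 12-month effect with a confidence interval only if a low-powered interaction test is significant; otherwise one pooled 6/12-month effect is reported

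*SAP*

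**What the plan says.** Section 10 of the SAP, headed as additional exploratory analyses, states that the "mean change from baseline in systolic blood pressure over 12 months will be estimated using a linear mixed model". The model has arm, visit, their interaction, the randomisation strata and baseline SBP. The reason given for the interaction is clear: "The inclusion of the interaction term allows the effect of the intervention to differ over time". If the term is not significant at the 0.10 level, however, "we will drop it from the model and estimate the overall effect of each intervention (vs SOC) on the change in systolic blood pressure".

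The effect on blood pressure control over 12 months "will be estimated using random effects logistic regression", with the same rule: if the interaction is not significant, "we will drop it from the model and estimate the overall effect of each intervention on the blood pressure control pressure during the trial".

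Elsewhere in the SAP, section 9.1 summarises SBP and its change by arm at both visits, but its between-arm estimate and interval are for 6 months. Section 9.2 tabulates control by arm at both visits, and its stated objective is control at 6 months. Section 2 defers sustainability to a separate analysis plan, which is not among the documents.

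**The concern.** The data decide which quantity is reported. If the interaction survives, the reader gets a 6-month and a 12-month effect. If it does not, the reader gets their average, with an interval that takes no account of the choice. A non-significant result from a test with little power does not show that the two effects are equal.

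At stake is the reading of durability. If part of the 6-month benefit has gone by 12 months, the pooled figure lies above the true 12-month effect, and a reader who takes it as the effect at the end of follow-up will be too optimistic. The 12-month result matters to the project: under Aim 3, the protocol feeds SBP and control at 6 and 12 months into the cost-effectiveness model, and its Table 4 lists SBP change from 6 to 12 months as a sustainability measure.

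**Working it through.** **Inputs from the documents.** 258 enrolled per arm, 20% loss, SD 19 mmHg, baseline-to-follow-up correlation 0.5, alpha 0.025, 80% power, 5 mmHg (SAP section 6 and Table 1); 206 analysed per arm (protocol Table 2).

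**Assumptions not in the documents.** The size of any waning, and the correlation r between the 6- and 12-month residuals after baseline adjustment, taken as 0.4 to 0.6. With a baseline correlation of 0.5 at both visits, the raw visit correlation is 0.25 + 0.75r, so this range corresponds to 0.55 to 0.70.

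**1. The plan's own figure.** n = 2(z₀.₉₈₇₅ + z₀.₈₀)² × SD² × (1 − 0.5²) / 5² = 2 × (2.241 + 0.842)² × 361 × 0.75 / 25 = 205.9, so 206; 206 / 0.8 = 257.5, so 258. This reproduces the plan. The residual SD is 19 × √0.75 = 16.45 mmHg.

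**2. Standard errors, 206 per arm with both visits.**
- Effect at one visit: 16.45 × √(2/206) = 1.62.
- Difference between the visit effects: 1.62 × √(2(1 − r)) = 1.78 at r = 0.4 and 1.45 at r = 0.6.
- Pooled effect, which here is the equal-weight average: 1.62 × √((1 + r)/2) = 1.36 and 1.45.

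**3. Probability of dropping.** For waning w and se_d the second standard error above, P = Φ(1.645 − w/se_d) − Φ(−1.645 − w/se_d). For 5 to 3 mmHg, w/se_d is 1.13 at r = 0.4 and 1.38 at r = 0.6, giving 0.70 and 0.60. For 5 to 2 it is 1.69 and 2.07, giving 0.48 and 0.34.

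**4. Coverage once dropped.** The pooled estimate centres on the mean of the two visit effects, so it overstates the 12-month effect by b = w/2: 1.0 mmHg for 5 to 3, and 1.5 mmHg for 5 to 2. With equal precision at the two visits, the average and the difference are independent, so the pre-test does not alter the distribution of the pooled estimate. Coverage of the 12-month effect is Φ(1.96 − b/se_p) − Φ(−1.96 − b/se_p), with se_p the pooled standard error. For 5 to 3, b/se_p is 0.74 and 0.69, giving 0.886 and 0.894. For 5 to 2 it is 1.11 and 1.03, giving 0.80 and 0.82. For the 6/12-month average, b is zero and coverage is 95%.

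**5. All trials together.** Add the probability that the term is kept and the 12-month interval covers, by integrating over the joint normal distribution of the two visit estimates.

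| True 12-month effect (5 mmHg at 6 months) | Term dropped | 12-month coverage if dropped | 12-month coverage, all trials |
|---|---|---|---|
| 5 (no waning) | 90% | 95% | 94% |
| 3 | 60–70% | 89% | 90–91% |
| 2 | 34–48% | 80–82% | 88–91% |
| 0 (complete loss) | 4–12% | 55–59% | 91–94% |

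**6. Sensitivity.** The SAP does not say whether the three-arm interaction is tested jointly or per arm. A joint 2-df test with both interventions waning equally gives drop rates of 61–70% (5 to 3) and 32–48% (5 to 2). A simulation of the random-intercept model, with 258 per arm, raw visit correlation 0.5, 20% missing at month 6 and an assumed 28% at month 12, gives for waning from 5 to 2.5 mmHg: dropped 64%, coverage 83% when dropped and 87% overall. Always keeping the interaction gave 94.5–95.3% across the simulated scenarios. The logistic model was not simulated; the rule is the same, but no size is claimed for it.

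**The case against.** The best defence is that the SAP does not call the pooled figure a 12-month effect. It calls it an overall effect during the trial, and the pooled interval covers the 6/12-month average at about 95%. This stands: a reader might infer that the pooled intervals are simply too narrow, and for the quantity the SAP names they are not. The shortfall exists only when the result is read as the 12-month effect.

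Three other points also stand:
- The analyses are exploratory, and the 6-month primary and secondary analyses do not use the rule.
- The summaries by arm in sections 9.1 and 9.2 would show a decline, so waning is not hidden. They do not give a 12-month contrast with an interval.
- The average harm is modest. Bias over all trials is about 0.2–0.4 mmHg, at most a quarter of the 1.62 mmHg standard error. For 5 to 3 mmHg, root mean squared error is about 1.72 under the rule against 1.62 with the term kept. Complete loss of effect is usually detected.

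A reader might also infer that durability is compared between arms nowhere else in the project. The documents do not support that, because sustainability has its own plan, which was not available.

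Finally, a reader might think the random-effects odds ratio is inflated. For control of 30% against 45%, the marginal odds ratio is (0.45/0.55)/(0.30/0.70) = 1.91, and the subject-specific one is about 2.3 to 3.7 for an assumed latent ICC of 0.3 to 0.7. That is a difference of scale between two valid measures, not an error.

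**Conclusion.** The concern holds for the 12-month effect in this SAP. A model-based 12-month comparison with an interval depends on a pre-test that misses moderate waning in roughly a third to two thirds of trials: 60–70% for 5 to 3 mmHg and 34–48% for 5 to 2 mmHg. When it misses, the pooled estimate is too favourable for month 12 by half the waning, and its interval contains the true 12-month effect about 89% and 80–82% of the time respectively.

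These sizes rest on the plan's SD, correlation and analysed n, and on assumed waning and between-visit correlation. With no waning the rule does almost no harm. It does not call the trial's main conclusions into question. It is worth correcting because the loss is avoidable and the model needed is already specified.

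**What to change.** Delete the two sentences in SAP section 10 that remove the interaction. Keep it whatever its p-value, and always report the 6-month and 12-month contrasts of each intervention with SOC, with confidence intervals, for SBP and for blood pressure control. Give the equal-weight average of the two as the overall effect, labelled as such. If an interaction p-value is shown, state whether it is a joint or a per-arm test.

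Optionally, report standardised proportions and differences from the random-effects logistic model, since its odds ratio is not on the same scale as that of section 9.2.

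No new data or model are needed. The cost is precision in the month-12 statement: a standard error of 1.62 mmHg against about 1.36–1.45 for the pooled effect, or a 95% half-width of 1.96 × 1.62 = 3.2 mmHg against 2.7–2.8. The pooled estimate remains available as the labelled average.

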We will summarize participant sociodemographic and clinical characteristics at baseline in all three arms. We will use linear regression to estimate the difference between arms, and its 95% confidence interval (CI), in systolic blood pressure at 6 months, adjusted for baseline systolic BP. We will use logistic regression to estimate odds ratios (OR) and 95% CIs for the impact of the intervention on the proportion of participants who achieve blood pressure control (<140/90) at 6 months.

Characteristics of individuals who are lost to follow-up will be tabulated by study arm. Since study nurses will visit all participants at home to measure blood pressure at 6 and 12 months, we do not expect there to be differential loss to follow-up between arms. In the primary analyses, participants with missing data at 6 months will be excluded. In sensitivity analyses, those with missing measurements will be considered to have no change in systolic BP and uncontrolled BP. Missing values may also be imputed using multiple imputation.

In pre-planned secondary analyses, we will fit regression models stratified by sex (to assess for sex as a biologic variable), age strata, socioeconomic status and baseline co-morbidities (i.e. obesity and HIV) to determine sub-group effect sizes and test the significance of an interaction term between sub-groups and the intervention to assess for effect modification.

A detailed statistical analysis plan will be prepared before the data are examined by treatment arm.

M. Risks, Protection from Risks and Benefits to Study Participation in Aim 2

a. Risks and Protections

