For participants who cannot be reached to schedule 6 or 12 month visits, a study staff member will attempt a home visit to collect outcome data.

6. Sample size

Based on patient attendance data from the two PHCs in our study in 2020, we estimate that there are over 1000 individuals with uncontrolled hypertension and thus eligible to enrol in the trial. We anticipate mean blood pressure at baseline will be 150/95 mmHg, with a standard deviation (SD) of 19 mmHg, based on previous studies. With 774 participants enrolled (258 per arm), we will have 80% power to detect a 5 mmHg difference between arms in the change of blood pressure from baseline to 6 months, assuming 20% loss to follow-up, a correlation between baseline and follow-up measurements of 0.5, and an alpha of 2.5% to account for multiple testing with comparisons between the SOC and both intervention arms (Table 1).

This same sample size will also give us greater than 80% power to detect an increase in the proportion of participants who achieve BP control (defined by a systolic BP <140 mmHg and diastolic BP <90mm Hg) at 6 months from 30% in the SOC arm to 45% in the interventions arms, or from 40% in the SOC to 56% in the intervention, also allowing for an alpha of 2.5% to account for multiple testing.

Table 1. Differences in change from baseline that can be detected with 80% power

N enrolled per arm	Loss to follow-up	Difference that can be detected (mmHg)	Standard deviation	Correlation between observations	Power
330	20%	5.0	19.0	0.20	80%
258	20%	5.0	19.0	0.50	80%
148	20%	7.5	19.0	0.20	80%
115	20%	7.5	19.0	0.50	80%

7. Definitions and analysis populations

All analyses will be conducted using the intention-to-treat principle, where all randomised participants will be included in the analysis regardless of adherence to the intervention.

All analyses of blood pressure will use the average of the second and third measurement as the blood pressure measurement for that visit. In the primary analyses, participants who are missing any of the three measurements will be considered to be missing blood pressure data for that visit. As a sensitivity analysis, individuals with fewer than three measurements will be included, using the average if there are two, or a single measurement if only one is available.

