9.1 Primary objective

The primary objective of the trial is to examine the effect of the interventions on the change from baseline in systolic blood pressure 6 months after enrolment. The mean

and SD systolic blood pressure, and the mean and SD change from baseline, at the 6 and 12 month visits will be summarised by treatment arm.

Linear regression will be used to estimate the mean difference, and its 95% confidence interval (CI), between each intervention and SOC (i.e. CBPM vs SOC and eCBPM+ vs. SOC) in the change from baseline at 6 months. The response variable will be systolic blood pressure at 6 months; the model will include treatment arm, clinic, active use of hypertension medication and baseline systolic blood pressure.

In secondary exploratory analyses, we will adjust for baseline values of age, sex, body mass index (BMI), smoking status and HIV. In separate models, we will fit an interaction term between the treatment arm and sub-groups of interest (e.g. sex, age group, co-morbidities) to examine sub-group effect sizes and potential effect modification.

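### SAP section 10 tests whether the SBP effect varies with baseline SBP and age only at single cuts (160 mmHg, 60 years), which loses efficiency if the modification is gradual

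*SAP*

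**What the plan says.** SAP section 10 states that consistency of the effect on the primary outcome "will be assessed in the following pre-specified groups, using a statistical test of interaction". Two of the four groupings are cuts of continuous variables: "Individuals with systolic blood pressure (SBP) ≥ 160 mmHg and those with SBP < 160 mmHg at enrolment" and "Individuals aged ≥ 60 years and < 60 years". The other two, sex and self-reported HIV status, are categorical already. Each subgroup gets an estimate and a 95% CI, and each grouping an interaction p-value.

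The other interaction wording is also in terms of groups. SAP section 9.1 says "we will fit an interaction term between the treatment arm and sub-groups of interest (e.g. sex, age group, co-morbidities", and the protocol's Aim 2 Analysis Plan refers to "age strata, socioeconomic status and baseline co-morbidities (i.e. obesity and HIV) to determine sub-group effect sizes".

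In the primary model, by contrast, baseline SBP enters ungrouped: "the model will include treatment arm, clinic, active use of hypertension medication and baseline systolic blood pressure" (SAP section 9.1). The planning values are in SAP section 6: "We anticipate mean blood pressure at baseline will be 150/95 mmHg, with a standard deviation (SD) of 19 mmHg, based on previous studies". Neither document gives a power, an expected size or a specific alpha for any interaction, an age distribution, or a reason for choosing 160 or 60.

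**The concern.** Baseline SBP and age are available as continuous values, and baseline SBP is already in the model that would carry the interaction. A single cut treats 141 and 159 mmHg as the same and 159 and 160 as different. If benefit rises steadily with baseline SBP, a two-group comparison uses only part of the evidence for that trend.

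Interaction tests in a trial sized for a main effect are weak to begin with. Weakening them further makes a non-significant p-value more likely when a graded effect exists. Because the analysis is framed as an assessment of consistency, such a p-value is easily read as showing that the effect is uniform.

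**Working it through.** **Inputs.** From SAP section 6: baseline mean 150 and SD 19, difference 5 mmHg, correlation 0.5, loss 20%, 258 enrolled per arm, alpha 2.5% (two-sided reproduces the stated size). Assumed, because the documents are silent: the shape of the SBP distribution, the age distribution, the form and size of the interaction, and 80% power for the continuous test as a reference point. All power figures are for one intervention against SOC. Section 10 does not say whether the Bonferroni level of section 9 applies to interactions, so both 5% and 2.5% are shown.

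**Step 1: the plan's own sample size.** With variance 19² × (1 − 0.5²) = 270.75, n = 2 × (2.241 + 0.842)² × 270.75 / 5² ≈ 206 analysed per arm, and 206 / 0.80 ≈ 258 enrolled. The same formula gives all four rows of SAP Table 1 (330, 258, 148, 115). The claim "we will have 80% power to detect a 5 mmHg difference between arms in the change of blood pressure from baseline to 6 months" therefore reproduces, with baseline-adjusted variance.

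**Step 2: information kept at the SBP cut.** For a linear interaction with a normal modifier, the share kept is the squared correlation between the modifier and its indicator, φ(c)² / [p(1 − p)].
- c = (160 − 150) / 19 = 0.526, so p = 29.9% are at or above 160.
- Kept: 0.347² / (0.299 × 0.701) ≈ 0.575. Lost: 42.5%.

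**Step 3: power.** With the continuous test at 80%, the cut test has power Φ[(z_α + 0.842) × √0.575 − z_α].
- Two-sided 5%: Φ(2.802 × 0.759 − 1.960) = 56.6%, a loss of 23.4 points.
- Two-sided 2.5%: Φ(3.083 × 0.759 − 2.241) = 53.9%, a loss of 26.1 points.
- Simulation of the baseline-adjusted model (206 per arm, 4,000 runs), continuous against cut: 79.8% against 54.4% at 5%; 77.4% against 51.5% at 2.5%.

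**Step 4: sensitivity to the assumptions, starting from 80% power.**

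| Assumed distribution | Information lost | Power of cut test at 5% |
|---|---|---|
| SBP normal, 150/19 | 42.5% | 57% |
| SBP right-skewed, same mean and SD | 36–39% | 59–61% |
| SBP normal, truncated above 140 | 33% | 63% |
| Age normal, mean 60 | 36% | 61% |
| Age normal, mean 55, SD 12–15 | 39–40% | 58–59% |
| Age normal, mean 50, SD 12–15 | 46–51% | 50–54% |
| Age normal, mean 45, SD 12–15 | 56–65% | 38–46% |
| Age uniform, 18–90 or 30–85 | 26–27% | 67–68% |

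For a normal variable the best case is a cut at the median, which keeps 0.399² / 0.25 = 63.7%; hence at least 36% is lost if age is normal.

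**Step 5: size of the interaction.** The standard error of the interaction slope is √270.75 / (19 × √(206/2)) = 0.0853. A slope of 0.24 mmHg per mmHg of baseline SBP gives 0.24 / 0.0853 = 2.81, hence about 80% power on the continuous scale. At half that slope (0.12), power is about 29% continuous and 19% with the cut, a loss of 10 points.

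**Step 6: if the truth is a step at 160.** The squared correlation is symmetric, so the order reverses. In simulation at 5% the cut test has 79.6% and the linear test 55.4%.

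**The case against.** The strongest reply is that these are pre-specified groups in a section headed as exploratory. Fixing the cuts in advance guards against picking them from the data. Effects with confidence intervals will be shown, so readers do not depend on a p-value alone. The cuts play no part in the primary model, its alpha or the sample size. All of this stands.

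The size of the loss also depends on choices the documents do not make. Starting from 80% power shows it close to its largest. A slope of 0.24 means 0.24 × 19 ≈ 4.6 mmHg per SD of baseline SBP, which is large beside a design difference of 5 mmHg. For weaker modification both tests have little power and the change recovers less. Under a step at 160 the planned test is the better one. These points limit the claim. They do not favour testing at the cut alone, since the documents give no reason to expect a step.

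A reader might infer more than the documents support:
- That the loss exceeds 20 points in general. Under truncation above 140 it is 17, and for age cut at the median of a normal distribution it is 19 at 5%.
- That the loss for age is known. No age mean or SD is given, and plausible assumptions run from about 26% to 65%.
- That the plan misses a power target. It sets none for interactions.
- That scale-up would be mistargeted. Nothing in the documents ties targeting to this test; the protocol's cost-effectiveness modelling uses individual-level data.

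**Conclusion.** The point holds as a modest improvement to an exploratory analysis. Effect modification by baseline SBP and age is tested only at one cut each. For SBP, with the plan's mean and SD, a normal shape and a roughly linear interaction, about 42% of the information is lost, and 80% power becomes about 57% at two-sided 5% or 54% at 2.5%. The loss is about 33% and 17 points if SBP is truncated above 140. That is a limiting case, because the SAP also admits people on diastolic pressure alone. For age only a conditional statement is possible: at least 36% if normal, less if closer to uniform. The 80% starting point is a reference assumption and not a figure from the plan. The primary estimate and its test are unaffected.

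**What to change.** In SAP section 10, add two interaction tests to the section 9.1 model: arm by continuous baseline SBP and arm by continuous age. Make each linear, with a restricted cubic spline as a check of shape, and plot the estimated effect with its 95% CI across the observed range. Keep the planned ≥160/<160 and ≥60/<60 estimates and their interaction p-values alongside. Sex and HIV status stay as they are.

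The cost is a short SAP amendment and a few lines of code, with no new data, visits or participants. There are two drawbacks. It adds two more exploratory tests per comparison with SOC. And the linear test alone would be clearly weaker, by about 24 points from 80%, if the true modification were a step at the cut, which is why the planned groups should remain.
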